NIHR	National Institute for Health Research
NRES	National Research Ethics Service
OME	Otitits Media with Effusion
QALY	Quality Adjusted Life Years
QoL	Quality of Life
RCT	Randomised Controlled Trial
REC	Research Ethics Committee
RN	Research Nurse
TADAST	Two alternative Auditory Disability And Speech reception Test
TMG	Trial Management Group
TSC	Trial Steering Committee

SYNOPSIS

Study Title	An open randomised study of autoinflation in 4-11 year old school children with otitis media with effusion (OME) in primary care. (AIRs: AutoInflation Randomised study)
Internal ref. no.	09/01/27
Study Design	Open randomised controlled trial with two arms: autoinflation and standard care
Study Participants	School children aged 4-11 years old with glue ear in at least one ear
Number of Participants	294
Planned Study Period	Pilot study: July 2010 to December 2010 Main study: 3 years duration
Primary Objective	Assess the clinical effectiveness of autoinflation in resolving OME at 1 month
Secondary Objectives	Assess the clinical effectiveness of autoinflation in resolving OME at 3 months
	 Assess the cost effectiveness of autoinflation: in terms of the cost per additional child achieving resolution of OME at 1 and 3 months; and also in terms of cost per QALY.
	Describe the experience of using autoinflation, including nurse observed competence and reported compliance and develop an easy to use training protocol for every day practice.
Primary Endpoint	Tympanometric resolution in at least one affected ear per child at 1 month, defined as conversion of the B-type highly predictive of effusion to either an A or C1 type i.e. back to normal pressures.
Secondary Endpoints	Study specific questionnaire at 1 and 3 months, weekly diaries up to 3 months (to record days with reported hearing loss and earache, as well as recording periods of remission and recurrence)
	Tympanometric resolution in at least one affected ear per child at 3 months, defined as conversion of the B-type highly predictive of effusion to either an A or C1 type i.e. back to normal pressures.
	OMQ-14 a functional health status measure and study specific questionnaire of NHS resource use - self-administered at 3

Intervention	Short study-specific questionnaires at 1 and 3 months to evaluate compliance, positives/negatives of device. Record of nurse assessments at 1 and 3 months. Autoinflation
	months, Health Utilities Index at 1 and 3 months plus a study specific questionnaire on health resource use including recurrence, referral etc at 6 months.

1. PLANNED INVESTIGATION

1.1 Aim

The main aim of this proposed randomised study is to evaluate whether a standard manufactured autoinflation device (Otovent) is an effective treatment for OME ("glue ear") in children in an NHS primary care setting. Instruction and support in use of the device will be given to both parent and child but is limited to a brief intervention which could be feasibly delivered by a primary care nurse. The main clinical outcome is resolution of OME assessed objectively by tympanometry.

1.2 Research objectives

- i). Assess the clinical effectiveness of autoinflation in resolving OME at 1 month (primary outcome) and 3 months (secondary outcome).
- **ii).** Assess the cost effectiveness of autoinflation: in terms of the cost per additional child achieving resolution of OME at 1 and 3 months; and also in terms of cost per QALY.
- **iii).** Describe the experience of using autoinflation, including nurse observed competence and reported compliance and develop an easy to use training protocol for every day practice.

1.3 Design

The proposed design is a pragmatic two-arm trial. Children randomised to the intervention group will start Otovent treatment immediately, whilst treatment in the control group will be delayed until the end of a 3 month comparison period. Children in both trial groups will undergo tympanometry at baseline, 1 and 3 months but usual clinical care will not be otherwise constrained. In the intervention group, children with normal tympanometry in both ears at 1 month will discontinue autoinflation whilst those with persisting OME will be encouraged to continue for up to two further months.

The intervention will be offered to control children with residual tympanic dysfunction at the end of the 3 month comparison period as we believe it will substantially increase recruitment to the study. The main study period up to 3 months will evaluate the additional benefit over usual care of a standardised purpose manufactured autoinflation device (Otovent) in improving OME, in school aged children in primary care, as assessed by a more objective method (tympanometric resolution) than history, at both1 and 3 months.

We will assess cost effectiveness at the end of the randomised 3 month active monitoring period as the health economic main outcome in terms of costs and QALYs, and will also include resolution of OME in the shorter term (1 month), and use an extrapolated scenario analysis including the data from the 6 month audit for longer term projections of costs.

A period of three months active monitoring (watchful waiting) has been chosen as it is best current practice. Good clinical practice also requires that children deemed as severe or protracted at the outset may need to be referred for surgery immediately and excluded from the trial; it is envisaged that this group will be very small.

2. EXISTING RESEARCH

2.1 Introduction

Otitis Media with Effusion (OME) is the commonest chronic condition of childhood and the commonest reason for childhood surgery. It is a collection of fluid behind the ear drum without inflammatory signs, ¹ and when present for 6 weeks or more is often called "glue-ear". OME can lead to significant hearing losses, especially when both ears are affected, and may have a significant and wide impact on the child's life and development.^{2,3,4}

The majority of children are seen in general practice, approximately 130,000 per year.⁵ A further analysis of these General Practice Research Database records up to 2008 suggests that the incidence for all types of otitis media in children has stabilised since 2001.⁶ By the age of 4 years, as many as 80% of children will have had at least one episode of OME. Most episodes resolve naturally with an average duration of 6-10 weeks, with just 10% of episodes lasting a year or more.^{4,5,7,8} Within the broad picture of the natural history there are a substantial number of children that do not have effusions that resolve quickly, remain a cause for concern, pose management issues for general practice, contribute to quite variable referral rates, and leads to surgery in about 1-5 per 1000 children per year (grommets).⁹ The scale of the problem of OME in society is likely to increase in the near future. Firstly as an anticipated sequelae of influenza in children,⁸ and secondly a 2009 Office of National Statistics report has highlighted a rise in the UK fertility (birth) rate from a record low in 2001(1.63) to a record high in 2008 (1.96).¹⁰ These factors are likely to lead to an increased clinical load in the near future, and thus makes the search for evidence for pragmatic interventions for OME in primary care both timely and apposite.

A recent NICE review has found no proven effective medical treatments that are applicable in primary care. ¹¹ Because OME might usually be expected to resolve naturally, watchful waiting for 3 months or *active monitoring* as it is better described, is now an established clinical recommendation. ^{11,12,13} Active monitoring of affected children might be performed in either primary or secondary care, although it has been questioned if GPs have the techniques for active monitoring with only about 5% of practices having the equipment, and also whether use of tympanometry in this setting would also lead to over referral. ¹⁴ However a recent study in primary care from our group has demonstrated that with appropriate training tympanometry is eminently feasible in this setting with low referral rates observed. ¹⁵ During periods of reasonable expectation of natural resolution of the condition, temporising medical management is frequently given in general practice, and this often includes antibiotics, decongestants, and anti-histamines, all of which have been shown to be clinically ineffective. Furthermore these interventions are associated with substantial NHS costs and a number of

harms and other disadvantages.¹¹ A recent large study of topical intranasal corticosteroids for 3months in children aged 4-11 years has also proved an ineffective method of temporising treatment in a primary care setting.¹⁵ Clinical trial evidence for an effective non-surgical intervention that could be applied in primary care where the majority of children are initially seen and managed thus remains an important research priority. A low cost, safe and effective treatment applicable in primary care, could also serve to benefit by improving patient and parent satisfaction, and general adherence with and support for the recommended monitoring process. The simple autoinflation treatment that is proposed in this trial has no known harms to date, and has potential to provide three important health benefits: i) a reduction in antibiotic prescribing and consequent risk of antibiotic resistance, ^{16,17} ii) a reduction in hospital referral and need for grommet surgery, ^{11,13}; iii) a reduction in potential learning problems from deafness associated with OME and tympanosclerosis associated with surgery.^{3,18,19}

2.2 Clinical trial evidence for autoinflation

Autoinflation is a promising technique with some preliminary efficacy and effectiveness demonstrated in several small hospital based trials reported in two meta-analyses. 20,21 In total 6 clinical trials were found suitable to be included in Cochrane. 22-27 A literature search (search date March 2009), which is an update of the original Cochrane systematic review, has been performed using the standard Cochrane search method as described in full in reference 20. Two additional references to clinical trials were found of which one was a completed RCT carried out on a total sample of 40 children.²⁸ Good results were shown in the compliant group from one small hospital study that involved a total of 85 children aged 3-10 years.²² Different methods of autoinflation using Valsalva techniques, party blowers, and face masks as well as purpose manufactured devices are considered in both meta-analyses. The balloon technique (Otovent) and the Ear popperTM (operating like a syringe driver applied to the nose) are the only two purpose manufactured standardised delivery devices and appear also to be the most promising studies so far in terms of beneficial odds ratios. Four small studies used the balloon technique (Otovent) intervention as the method for autoinflation. One was an independent study done in UK secondary care, 22 one was based on a Danish sample, 23 a third hospital study remains unpublished (Suonpaa and Grenman). Combining these three trials with the most recent small trial,²⁸ gives a combined potentially homogeneous total of 336 children, but dominated by secondary care studies. For the tympanometric outcomes at 1 month the odds ratio based on all four studies was 2.4, but was not significant. The Cochrane authors although finding a large effect size for the autoinflation method overall with a Relative Risk of Improvement of 2.47 for tympanometric outcomes reported confidence intervals going through1 (0.93 to 6.8). The authors concluded there was insufficient evidence as yet to recommend widespread use in general practice, and called for a larger-scale pragmatic trial with longer term follow-up than 1 month.²⁰

A subsequent up to date (Sep 11, 2009) Medline search has revealed no further relevant studies. Thus the clinical efficacy and effectiveness of autoinflation in a primary care UK population remains untested and requires full evaluation before use in the NHS. Primary care is the best setting to evaluate effectiveness of autoinflation, because most children with OME are seen in primary care, it is increasingly clear that there are as yet no satisfactory treatments in this setting, 11,15,29,30 and lack of a good non-surgical intervention is

version 5, 25-08-11

probably a major factor fuelling the substantial rates of referral for childhood surgery, which is thus far the only proven effective treatment. There are no known harms associated with autoinflation, with higher respiratory tract infection rates noted in the control groups in two studies, making it unlikely that the increased pressure in the nose during autoinflation spreads infections. Perhaps compliance is the major potential weakness with this technique, and it can probably only reliably be performed in school aged children (4-5 years and older). Autoinflation by Otovent (£7) has the advantage of being considerably less costly than the Ear popper (\$200) and with better preliminary evidence than just the 1 manufacturer randomised study in 94 children for the ear popper, thus making the nasal balloon method the intervention of choice for further evaluation. No clinical trial evaluation of the treatment method (autoinflation), which has considerable pragmatic potential to help a great many children, has been done thus far from any primary care setting, with the few studies to date all being small and hospital based. Provided the effect size in primary care is likely to be larger than in secondary care due to the nature of the effusion (see mechanism considerations below).

In summary, the current evidence suggests there may be a 2.4 times higher rate of short-term tympanometric cure in children using a purpose manufactured balloon (Otovent device) than in controls.^{20,28} The combined studies however did not provide a definitive answer, all lacked intermediate and long-term follow up, and were investigated in largely selected secondary care populations.

2.3 A description of the technology; some mechanism considerations; and possible effect on health status.

Autoinflation is a self administered method that aims to insufflate the Eustachian tubes with air, improves tubal ventilation and corrects the negative middle ear pressures often observed in children with glue ear - thus leading to recovery. Autoinflation has probably been done in some form from antiquity most likely as the Valsalva manoeuvre. This is done by trying to do a forced exhalation by contracting the diaphragm and abdominal muscles when the mouth is closed and the nose pinched to try and make the ears "pop" as done by divers or on aeroplanes to equalise the pressure in the ear with atmospheric pressure. Not all children can do this and the most promising way for children to autoinflate effectively is probably by blowing up a balloon through the nostril. This must be done regularly (e.g. x2 or x3 times each day) according to trial evidence, with careful and appropriate training of guardians and children required.

The proposed study technique involves blowing out through each nostril in turn into a purpose fitted connector device (nasal tip or nozzle) with a balloon attached. The pressure generated to inflate the balloon is equivalent to about 30 inches of water pressure, and aids passive opening of the Eustachian tubes (the critical opening pressure required to introduce air into the middle ear reduces as the dimensions of the Eustachian orifice increases with the child's age, so the technique is likely to be more effective in older children as well as easier to do). The introduction of air into the middle ear has been shown to improve or normalise negative middle ear pressure in children performing the technique.²³

The observed transience of improved pressure changes in the middle ear from the autoinflation method has been questioned as a sufficiently adequate explanation for any therapeutic mechanism, with what appears to be singular theoretical reliance on restoration of tubal function (for a condition of mixed aetiology). The beneficial effects of changes in gas composition e.g. of small rises in oxygen tension in the middle ear (associated with improved middle ear ventilation over time), may also be theoretically important however, and may fit with ongoing research into the role of hypoxia in some genotypes, in particular the MRC Jeff mouse genetic model of otitis media. Autoinflation may also improve natural drainage by dislodging any mucus plugs blocking the Eustachian tubes etc. The clinical trial evidence to date supports a distinct therapeutic effect from autoinflation in compliant groups, however unclear the theoretical mechanism (this also holds true for OME causation in general). A clinical trial applied earlier in the natural history in primary rather than secondary care (where effusions have developed to be more mucoid and tenacious) is *prima facie* more likely to be effective using this aerating technique and in preventing sequelae. Along with severity, relevant effect modifiers for this method may include child age/head size, and compliance frequency. Season was not found to be an effect modifier in a primary care study.

Otovent is already available on NHS FP10 prescriptions (cost £7.20 per month for adults, with children exempt). If the short-term cure suggested in the Cochrane review were realisable in everyday practice (see power calculation), our hypothesised estimate of the potential effect on health and clinical practice is a 70% reduction in antibiotic prescribing, a 30% reduction in GP re-consultations, and 50% reduction in hospital referrals with insertion of grommets.^{4,11}

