3. RESEARCH METHODS

3.1 Phase 1 pilot study.

The 12 month pilot study is already funded through the NIHR Primary Care School and is taking place in two Southampton area and two Oxford area practices over the coming Autumn/ Winter seasons of 2009/10. It is due to complete in April-July 2010. It is being performed because this is the first study of its type in primary care. We are using a moderate degree of new technology, *e.g.* tympanometry and a new mechanical technique for treatment in this setting. Also the new research practices require full training with the specific study material packages. The pilot aims for 28 children. We currently estimate uptake rates of 40% which we deem likely because all children confirmed with symptomatic and tympanometric OME will be offered a treatment and improved monitoring in addition to usual care (also there are no known side effects to this treatment). Basing the take-up on 40%, 112 children accepting screening from 280 invited through 4 practices, 25% of which will be eligible for randomisation on tympanometry will yield 28 children in the pilot trial. This pilot will allow confirmation of the trial uptake estimates of 40% with a 95% level of precision of ± 5.7%.

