3.1.2 Completed pilot study summary

The pilot work has i) demonstrated feasibility ii) demonstrated good study compliance with the technique and follow up iii) improved logistical assumptions e.g. trial uptake precision estimates, iv) provided useful consumer feedback, v) developed the study materials and information in a standard operating manual, vi) confirmed the original study power calculation and demonstrated a potential large effect size OR 4 95%CI 0.97 to 16.46, vii) added a new exclusion criterion viii) refined the randomisation method to be used to improve access- now web based with training support ix) developed a web based hearing disability outcome with evaluation of reliability for use as a trial outcome x) improved the trial management structure and costings.

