3.7 Exclusion criteria

- Children who need early referral as judged clinically, to include those known rarer cases with high risk
 of recurrence: Down's, cleft palate, Kartagener's, Primary Ciliary Dyskinesia, immunodeficiency
 states etc.
- 4 year old children not attending school at the time of screening, or children deemed by the nurse unable to comply with the technique of autoinflation.
- At study entry, children with a grommet already in place in an ear drum, or where the child has been referred or listed for ear surgery.
- Latex allergy (balloons are latex)
- A recent nose bleed in the past 3 weeks or more than one episode of nose bleeding over the past 6 months

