5. RISKS AND ANTICIPATED BENEFITS

As with all trials there is always a degree of risk to participants, however in this particular trial the risks are estimated to be extremely small. No side effects have been reported from current trials. The main theoretical side effect is an increase in upper respiratory infection due to air pressures generated in the nasal cavity equivalent to being submerged under 2-3 foot of water somehow spreading infected mucus up the Eustachian tubes. No such increase in infection rate has been noted in the trials so far and in fact the incidence of respiratory tract infection was observed to be higher in the control group in the only previous British study.²³

The fact that fluid behind the ear on tympanometry is found less commonly in treated groups in most trials to date also means that ear infections are likely to be less when using the device. The ICH-GCP guidelines for definitions of adverse events/reactions will be followed, and all adverse events/reactions will be recorded. The co-ordinating centre's standard operating procedure for safety reporting in studies not involving an investigational medicinal product will be fully complied with, including reporting of all serious adverse events (e.g. any unplanned hospitalisation) to the sponsor immediately, and as will all related unexpected serious adverse events. In addition to any expedited reports, annual safety reports will be submitted to the main REC.

Placebo treatment is not planned at all in this children's study. All children/guardian participants will be offered the intervention after 3 months of the study if they were not initially randomised to the +autoinflation arm, and the fluid/effusion has not gone away by that time.

Using the combinations of:"natural cure+ standard care +/- any treatment effect from adjunctive use of the device," constitutes possibly the best primary care approach currently available to evaluate. On the basis of the NICE 2009 guideline which recommends active monitoring for OME for 3 months, and states "autoinflation may be beneficial in older children". Although standard care will be fully detailed in the study there is no evidence for any significant effect of any of the commonly used treatments on tympanometric resolution. The level of trial care and aftercare will be thorough and, as proposed, will meet high standards.

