7.2 Secondary outcomes

All measures will be assessed at baseline (0), and 1 and 3 months post baseline (except the OMQ-14, designed to collect retrospective 3 month data and TADAST which will be performed at baseline and 1 month only).

- The difference in proportions of children showing resolution to A or C1 in at least one B (affected) ear per child at 3 months
- OMQ-14 a functional health status measure that is a derivative of the OM8-30 that is both pragmatic and predicts QoL well, and will be self-administered at baseline and 3 months (please see Appendix 2). The main measurement tools have been used in GNOME with validation. The OMQ-14 is a succinct standardised and responsive 14 item measure that looks at the quality of life, physical and developmental impact of OME. It records the previous 3 month history including frequency of respiratory tract infections which is the main theoretical adverse event (see above). Together with a brief resource use questionnaire (used in GNOME) and notes audit, it will collect useful adjunctive health economic information.
- Parents will be asked to complete short study-specific questionnaires at the above times for evaluation of: compliance; positives/negatives of device; being in a study; NHS resource use for economic evaluation; and also use weekly symptom and adverse event diaries collected at 1 and 3 months to prospectively collect data on the main areas of OME clinical impact. The diaries record days with reported hearing loss and earache, as well as recording periods of remission and recurrence. The diaries make use of Likert scales for symptoms as validated and used in other studies from our group. 36,40,41
- Hearing will also be assessed by using the web TADAST speech recognition in noise parent supervised (self-complete) test at baseline and 1 month. 38,42,43 Audiometry will not be included to assess hearing level in this trial because hearing level is not a known effect modifier, it's correct use is somewhat variable and unreliable in primary care because of factors such as those associated with child age and type of test, operator training issues, and high background noise levels confounding the results. Measures based on reported hearing difficulty (OMQ-14 questionnaire) and air conduction estimates from tympanometry have however been developed which can be also used in the analysis. 15

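### Nosebleed is treated as a risk at entry but is not named as a harm to ask about, so its reporting may differ between arms

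*Protocol*

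**What the plan says.** Four places in the Protocol describe the device's safety record in nearly the same terms:

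- Section 2.1: the treatment "has no known harms to date".
- Section 2.2: "There are no known harms associated with autoinflation".
- Section 3.1, on the pilot: "there are no known side effects to this treatment".
- Section 5: "No side effects have been reported from current trials".

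Section 5 then names one possible harm: "The main theoretical side effect is an increase in upper respiratory infection due to air pressures generated in the nasal cavity". Section 7.2 gives that harm a structured question, because the OMQ-14 covers the frequency of respiratory infections.

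Section 3.7 lists as an exclusion: "A recent nose bleed in the past 3 weeks or more than one episode of nose bleeding over the past 6 months". No reason is given, and nosebleed is mentioned nowhere else in the document.

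On collection, section 5 commits to recording every adverse event. Section 7.2 describes weekly diaries for symptoms and adverse events, collected at 1 and 3 months, and says of their contents: "The diaries record days with reported hearing loss and earache", together with remission and recurrence. Section 3.2.3 shows that both groups keep the diary, since both receive tokens for returning it. The same section describes a nurse's call at 2-4 days, at which untoward effects are noted, within its account of children randomised to autoinflation.

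**The concern.** The device is blown through each nostril three times a day (section 3.4) for one to three months. An exclusion for recent nosebleeds suggests that its authors foresaw nosebleed as a possible effect of such a device. Yet the section meant to set out the risks does not mention it, and no question about it is described.

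Nosebleeds can also occur without the device, so only a comparison between arms, with the same enquiry in each, can show whether the device adds to them. Families know their allocation (section 3.3). If nosebleeds reach the record only when a parent volunteers them, and one arm has an extra occasion to do so, a real excess could be missed or an apparent one created. An analysis plan cannot recover events that were never asked about, so this has to be settled in the protocol and the data collection forms.

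**Working it through.** The plan gives no figure on nosebleeds, so there is none to reproduce. The check is mainly a comparison of sections, followed by two illustrations on assumed rates.

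**1. Risk statements against eligibility.** Sections 2.1, 2.2, 3.1 and 5 report no harms or side effects known or reported. Section 5 names respiratory infection as the main theoretical one. Section 3.7 acts on nosebleed. The eligibility section therefore guards against something that the risk section leaves out.

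**2. Enquiry about harms, by arm.**

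| Source | Autoinflation | Control | Nosebleed named? |
|---|---|---|---|
| OMQ-14, baseline and 3 months (7.2) | yes | yes | no; respiratory infection is |
| Weekly symptom and adverse event diary (3.2.3, 7.2) | yes | yes | not among stated contents; form not shown |
| Nurse call at 2-4 days (3.2.3) | yes | none described | no |

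The call is the one step that is plainly unequal as written.

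**3. What unequal recording could do.** Expected recorded events = n × true rate × share recorded. Take n = 294/2 = 147 per arm, from the Synopsis total. The true rates and recorded shares below are assumptions; none comes from the documents. The true rate is the same in both arms.

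- True rate 5%, recorded 80% against 50%: 147 × 0.05 × 0.80 = 5.9 against 147 × 0.05 × 0.50 = 3.7.
- True rate 15%, same shares: 17.6 against 11.0.
- The true rate cancels from the ratio: 0.80/0.50 = 1.6. With 80% against 70% it is 1.14. With equal recording it is 1.0.

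A false difference needs a gap in recording between arms. Failing to name nosebleed does not create that gap by itself.

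**4. What a prompted item could show.** Normal approximation, two-sided 5%, n = 125 per arm (section 8.1), every event recorded:

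power = Φ{[|p1 − p2| − 1.96 √(2p̄(1 − p̄)/n)] / √[(p1(1 − p1) + p2(1 − p2))/n]}

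- 10% against 20%: (0.10 − 1.96 × 0.0452)/0.0447 = 0.26, power about 60%.
- 5% against 10%: about 32%.
- 20% against 40%: about 94%.

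These rates are also assumed, and the section 3.7 exclusion should lower the background rate. If all 125 device-arm children were asked and none reported a nosebleed, the one-sided 95% upper bound would be 1 − 0.05^(1/125) = 2.4%. The prompted item should therefore be reported as an estimate with its interval, not as a test.

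**The case against.** The strongest reply is that nothing here is contradictory and that collection is already provided for. Statements that no harms are known to date, or that earlier trials reported none, describe past evidence. A precautionary exclusion for a nasal device is compatible with them. Section 5 calls respiratory infection the main theoretical effect, not the only one. Every adverse event is to be recorded, both arms keep a weekly adverse event diary, and the wording of individual items normally belongs on the form. The contents named in section 7.2 are not said to be the full list. The call happens once, early in a three-month period, mainly for support, and the Protocol does not say that its notes enter any comparison between arms.

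Most of this stands. It rules out three stronger readings that a reader might draw:

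- *That nosebleeds will be reported unevenly.* The diary runs in both arms and may already ask about them.
- *That the pilot revealed a nosebleed problem.* Section 3.1.2 says only that the pilot "added a new exclusion criterion". It names neither the criterion nor the reason.
- *That parents are misinformed.* Section 5.1 promises information on possible risks, but the information sheet is not available to check.

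The reply does not remove two facts. The risk section omits something that the eligibility section acts on, and nothing in the Protocol guarantees that both arms are asked the same question about it.

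**Conclusion.** The point holds in limited form. The Protocol treats nosebleed as a risk at entry, does not name it as an anticipated harm, and describes an additional harm enquiry in one arm only of an open trial. Nosebleed reporting may therefore differ between arms. The safety wording and the exclusion are in tension and need reconciling; they do not strictly contradict each other.

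The size of any distortion cannot be derived from the documents. The ratios of 1.0 to 1.6 depend entirely on the assumed recording shares, and a single early call is weak evidence for a gap as wide as 80% against 50% over three months. The conclusion also rests on the diary form being unseen: if it already asks both arms about nosebleed in the same way, only the wording of the risk section and the choice of data source remain to be settled. This is a cheap improvement to harm reporting and leaves the primary outcome unaffected.

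**What to change.** 1. In section 5, name nosebleed as an anticipated adverse event beside respiratory infection. Reconcile the statements in sections 2.1, 2.2, 3.1 and 5 with section 3.7. Leave the exclusion as it is, and do not attribute it to the pilot.
2. Ensure that the weekly diary contains one prompted yes/no nosebleed item, worded identically and asked at the same times in both arms.
3. Report the proportion of children with at least one nosebleed by arm, with a 95% confidence interval for the difference, from that item only. Notes from the 2-4 day call can still serve safety oversight but should not feed this comparison.

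The cost is a diary line if it is not already there, a sentence in section 5 with matching edits elsewhere, and one table row. Prompting will raise the recorded number of nosebleeds in both arms, and the report should say so.
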